Study Protocol Summary

Title: Effect of Action Observation Training on Gait Variables and Global Cognitive Functions

ClinicalTrials.gov ID: NCT03522389

Date of the document: 10 April 2018

Brief Summary:

This randomized controlled trial investigates the effect of Action Observation Training (AOT) combined with gait training on gait variables and global cognitive functions in older adults diagnosed with mild cognitive impairment (MCI). The study compares outcomes among three

groups: AOT with gait training, gait training alone, and a control group.

Objectives:

1. To compare gait variables and global cognitive functions across the three groups before

training, after training, and at follow-up.

2. To assess changes in gait and cognitive functions over time within each group.

Study Design:

Single-blind randomized controlled trial with participants blinded to group allocation.

Participants:

Thirty-nine older adults (aged 60–80) with MCI were recruited from Mahidol University

Physical Therapy Center, Siriraj Hospital, and surrounding communities. Diagnosis based on

criteria from the National Institute on Aging and the Alzheimer's Association. Inclusion and

exclusion criteria apply. Informed consent was obtained prior to participation.

Methods:

Participants were randomly assigned (stratified by age and education) into three groups:

Action Observation with Gait Training (AOGT)

- Gait Training (GT)
- o Control group (no intervention)
- Gait variables were measured using a Force Distribution Measurement platform during single-task and dual-task walking conditions.
- Global cognitive function assessed by Montreal Cognitive Assessment (MoCA).
- Assessments conducted at baseline (T1), after 4-week of training (T2), and at 1-month follow-up (T3).

Intervention:

AOGT and GT groups receive 12 sessions over 4 weeks, including video observation, warm-up, gait training, cool-down, and stretching. The control group receives dementia education only and continues usual activities.

Statistical Analysis Plan

Data will be analyzed using IBM SPSS Statistics version 24, with statistical significance set at p < 0.05. Normality of data distribution will be assessed using the Kolmogorov-Smirnov test.

Given normally distributed data, parametric tests will be applied.

A two-way mixed ANOVA will evaluate the effects of group (intervention) and time on outcome variables, including their interaction (group × time). Repeated measures ANOVA was used to assess within-group changes across the three time points. Additionally, one-way ANOVA was used to compare mean changes between groups

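### Participant blinding is stated for the whole trial but cannot hold against the control arm; conclusions about action observation should rest on AOGT minus GT, once the GT video is clarified

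*Combined protocol and SAP*

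**What the plan says.** The Study Design section gives the blinding in one sentence: "Single-blind randomized controlled trial with participants blinded to group allocation". No arm is excepted.

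The Intervention section describes the trained arms together: "AOGT and GT groups receive 12 sessions over 4 weeks, including video observation, warm-up, gait training, cool-down, and stretching". Of the third arm it says: "The control group receives dementia education only and continues usual activities". The Methods section labels that arm as having no intervention. No sham or attention-matched sessions are described for it.

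The Brief Summary lists the arms as "AOT with gait training, gait training alone, and a control group", so GT appears there without video and in the Intervention section with it. The content of the video is not described for either arm.

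The title is "Effect of Action Observation Training on Gait Variables and Global Cognitive Functions". The Brief Summary gives the fuller aim: "the effect of Action Observation Training (AOT) combined with gait training on gait variables and global cognitive functions". Objective 1 is a comparison across all three groups.

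The between-group analyses visible in the Statistical Analysis Plan are a mixed ANOVA with a group × time interaction and a one-way ANOVA on mean changes. Both take the three groups together. No pairwise contrast is visible, but the text as supplied stops without a full stop straight after the one-way ANOVA.

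**The concern.** The blinding sentence claims a property that the described design does not have for two of its three pairwise comparisons. Someone who attends 12 gait-training sessions knows they are in a trained arm, and someone who attends none knows they are not. They may be unaware of the arm labels or the hypothesis, but the text does not say so, and that would be a narrower claim than blinding to allocation.

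This matters because expectation and contact time can affect performance outcomes. MoCA is performance-based, and walking depends on effort even when a platform records it. If the label carries into the report unchanged, readers will credit the contrasts with control with a protection they lack.

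The analysis adds to this. The three-group tests can be significant purely because control differs from the two trained arms. Such a result says nothing about what action observation adds to gait training, and it comes from the comparisons that cannot be participant-blinded.

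**Working it through.** **Step 1. Blinding, comparison by comparison, from the Intervention and Brief Summary sections.**

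| Comparison | What a participant can observe | Participant blinding |
|---|---|---|
| AOGT vs control | 12 training sessions vs education only | cannot hold |
| GT vs control | 12 training sessions vs education only | cannot hold |
| AOGT vs GT | same session format if both view a video; different if GT has none | possible only if both view a video |

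**Step 2. What AOGT minus GT measures.** Both arms receive the gait training, so it cancels in the difference. What remains is action observation, provided that GT participants do not also watch the trained gait actions. There are three cases:
- GT views a video without those actions: blinding is possible and the contrast isolates action observation.
- GT views a video with those actions: blinding is possible, but the contrast does not isolate it.
- GT views no video: the contrast is of action observation plus gait training against gait training alone, and it is not participant-blinded.

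The documents do not settle which case applies.

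**Step 3. Can a three-group test be significant with no action-observation effect?** The plan has no power calculation to reproduce. Its only sample-size figure is 39 participants. Assumptions: equal allocation, so 39 / 3 = 13 per arm; α = 0.05; AOGT and GT both exceed control by g SD of the change score and do not differ from each other.

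- Arm means are (g, g, 0) and the grand mean is 2g/3. The squared deviations are g²/9, g²/9 and 4g²/9, with mean 2g²/9.
- The noncentrality is 39 × 2g²/9. For g = 1 it is 39 × 2/9 = 8.67.
- The one-way ANOVA has 2 and 36 df, with critical value F = 3.26.

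| g (assumed) | Noncentrality | Chance that the ANOVA is significant |
|---|---|---|
| 0.5 | 2.17 | 23% |
| 0.8 | 5.55 | 51% |
| 1.0 | 8.67 | 72% |
| 1.2 | 12.48 | 87% |

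The values of g illustrate the mechanism. They do not estimate bias, because a real effect of gait training would produce the same pattern.

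**Step 4. Precision of AOGT minus GT on a change score**, in SD of change, two-sided 5%. The 95% CI half-width is t × √(2/n). The detectable difference at 80% power is from the noncentral t distribution.

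| n per arm (assumed) | Error term | df | t | Half-width | Detectable at 80% power |
|---|---|---|---|---|---|
| 13 | three arms pooled | 36 | 2.028 | 2.028 × √(2/13) = 0.80 | 1.13 |
| 13 | two arms only | 24 | 2.064 | 0.81 | 1.15 |
| 10 | three arms pooled | 27 | 2.052 | 2.052 × √(2/10) = 0.92 | 1.30 |
| 10 | two arms only | 18 | 2.101 | 0.94 | 1.32 |

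The rows with 10 per arm show the effect of some loss. The documents state neither the allocation ratio nor the numbers analysed.

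**The case against.** The strongest reply is that the documents never promise a conclusion specific to action observation. The fuller aim is action observation combined with gait training, and Objective 1 compares three groups, so three-group tests match the objective and AOGT versus control answers the stated aim. That stands. A reader might infer that an omnibus result will be reported as an action-observation effect, but no sentence says so. The point therefore applies to any such conclusion, which the title invites, and AOGT versus control remains legitimate for the package.

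Second, the plan may already name a contrast. Because the Statistical Analysis Plan text appears cut off, its absence cannot be treated as an omission. This also stands, but the blinding statement does not depend on it.

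Third, AOGT minus GT isolates action observation only under a condition that the text leaves open. That is right, and reconciling the GT description has to come first.

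Fourth, the platform limits rater judgement in the gait outcomes, and a trained arm against an untrained control can never be fully participant-blinded. Both are true. They argue for describing the blinding accurately, not for leaving the statement as it is. The design itself need not change.

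**Conclusion.** The concern holds in this form: participant blinding as stated cannot apply to AOGT versus control or GT versus control. For AOGT versus GT it is conditional on both arms viewing a video. Only the AOGT minus GT contrast can support a claim specific to action observation, and only if GT does not also observe the trained gait actions. It should be fixed, but it does not invalidate the trial.

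The blinding finding rests on the documents' own descriptions and needs no numerical assumption. The 72% figure assumes 13 per arm and a 1 SD difference from control. The ±0.80 SD half-width assumes 13 per arm.

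Three stronger readings are not supported:
- **That a measurable share of each result is biased.** The degrees of freedom divide evenly between AOGT versus GT and the trained arms versus control (2 and 2 of the 4 for group × time; 1 and 1 of the 2 for the one-way ANOVA). That counts dimensions and does not measure bias, and the documents give no basis for a bias figure.
- **That the outcome assessors are unblinded.** The text is silent on this.
- **That no comparison can be participant-blinded.** AOGT versus GT may be, depending on the GT video.

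**What to change.** 1. Reconcile the Intervention and Brief Summary descriptions of GT: state whether GT views a video and, if so, whether it shows the trained gait actions.
2. Restrict the participant-blinding statement to AOGT versus GT, if both view a video. Report both contrasts with control as not participant-blinded.
3. Rest any conclusion specific to action observation on AOGT minus GT, with its 95% CI, within the planned group × time and change-score analyses, and not on a significant three-group result. State the condition on the GT video beside it. If the full plan already names this contrast, refer to it. If the analysis has already been done (the text mixes past and future tense), label the contrast as post hoc.
4. Keep AOGT versus control as a non-blinded comparison of the combined package.

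The cost is wording and one contrast, applied to each outcome for which an action-observation claim is made; no new participants or data are needed. The downside is a less favourable blinding label and an imprecise contrast: with an assumed 13 per arm, a null result would not rule out a difference of practical size. That imprecision already exists in the design, and the interval makes it visible.

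### The mixed and repeated-measures ANOVAs use only participants seen at all three visits, so a missed visit discards observed data and may bias the group comparison, by an amount and in a direction that depend on why people drop out

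*Combined protocol and SAP*

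**What the plan says.** The Methods section sets three visits: "Assessments conducted at baseline (T1), after 4-week of training (T2), and at 1-month follow-up (T3"). The Participants section gives one count: "Thirty-nine older adults (aged 60–80) with MCI were recruited from Mahidol University". On allocation, Methods says "Participants were randomly assigned (stratified by age and education) into three groups"; no ratio is given.

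The Statistical Analysis Plan names three analyses:

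- Between groups over time: "A two-way mixed ANOVA will evaluate the effects of group (intervention) and time on outcome variables", together with the group × time interaction.
- Within groups: "Repeated measures ANOVA was used to assess within-group changes across the three time points".
- A one-way ANOVA of mean changes between groups. The visits that define the change are not stated.

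On software the SAP says only "Data will be analyzed using IBM SPSS Statistics version 24"; it does not name the procedure. Nothing in the document covers dropout, missing visits, imputation, an analysis population, or a likelihood-based model that would use partial records.

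**The concern.** Classical mixed and repeated-measures ANOVA delete listwise: a participant enters only with a full set of T1, T2 and T3 values. This comes with the named method, so a sentence acknowledging missing data would not recover the discarded results while the ANOVA stays.

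Two things are at stake. The first is precision. With about 13 per arm (assuming equal allocation), each discarded record counts. The second is validity. Two arms attend 12 training sessions and the third receives education only, so the reasons for missing a visit could differ by arm. If they relate to outcomes already observed, the completers in one arm are no longer comparable with those in another.

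There is also a problem of coherence. The group × time test would use completers only, while a T1-to-T2 change test could use more people. The plan does not say which set answers Objective 1, the comparison of the groups before training, after training and at follow-up.

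**Working it through.** **Inputs from the document:** 39 participants, three arms, visits T1, T2 and T3.

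**Assumptions, because the document gives no figure:** 1:1:1 allocation (13 per arm), the loss per visit, visit correlation 0.7 (equal between all pairs), and a true effect of 0.50 SD at T2 and T3. The plan has no sample-size derivation or dropout allowance to reproduce.

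**Step 1: who is kept.** With loss d at each visit, the number with T2 is 39 × (1 − d) and the number complete is 39 × (1 − d)².

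| Loss per visit | Have T2 | Complete T1-T2-T3 | T2 results discarded |
|---|---|---|---|
| 5% | 37.1 | 35.2 | 1.9 |
| 10% | 35.1 | 31.6 | 3.5 |
| 15% | 33.2 | 28.2 | 5.0 |

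The last column is what a model using all visits recovers at T2. People who leave before T2 and never return have only T1, and no model learns much about change from them.

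**Step 2: precision.** The standard error scales as 1/√n. At 10% per visit, the completer-only standard error is √(39/31.6) = 1.11 times that with all 39. The part recoverable at T2 is smaller: √(35.1/31.6) = 1.05, or about 5%.

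**Step 3: bias.** One training arm was compared with control in a large-sample simulation (one million per arm). Dropout occurs at T3, with a logit slope of 1 to 2 per SD where it depends on outcome. Estimates are differences in change from T1; the truth is 0.50 SD.

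| Why people miss T3 | Completer-only T2 effect | Completer-only T3 effect |
|---|---|---|
| Low T2 gain, training arm only (random in control), 10% | 0.56-0.60 | 0.53-0.59 across 10-20% |
| Same, 20% | 0.61-0.68 | as above |
| Same absolute gain rule in both arms, 10-20% in the training arm | 0.39-0.47 | below 0.50 |
| Low T2 level, training arm only, 10% | 0.53-0.54 | 0.50 |
| Completely random, or the same rule relative to each arm's own mean | 0.50 | 0.50 |

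In the third row the control arm gains less, so a fixed gain threshold removes more of its low gainers and the contrast shrinks.

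**Step 4: check on the T3 column.** Write ρ for the common correlation and take unit variances.

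- Dropout on T2 level: Cov(Y3 − Y1, Y2) = ρ − ρ = 0, so selection on Y2 does not shift the T3 change.
- Dropout on T2 gain: Cov(Y3 − Y1, Y2 − Y1) = ρ − ρ − ρ + 1 = 1 − ρ = 0.3, and Var(Y2 − Y1) = 2(1 − ρ) = 0.6. The ratio is 0.5, so the T3 bias is half the T2 bias.
- With T2 at 0.56 and 0.68, T3 should be 0.50 + 0.06/2 = 0.53 and 0.50 + 0.18/2 = 0.59, as simulated.
- With T2 at 0.39 and 0.47, T3 should be about 0.50 − 0.11/2 = 0.445 and 0.50 − 0.03/2 = 0.485.

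**Step 5: likelihood-based comparison.** Regressing T3 on T1 and T2 within arm and using everyone's T1 and T2 gives 0.50 SD at T3, and the T2 contrast is unaffected by T3 dropout. This is expected, because the simulated dropout depends only on observed values.

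**Step 6: scale.** The standard error of a pairwise change contrast with 13 per arm is √(2 × 0.3) × √(2/13) = 0.775 × 0.392 = 0.30 SD. A bias of 0.06-0.10 SD (the 10% case) is a fifth to a third of that. A bias of 0.11-0.18 SD (the 20% case) is about 0.4 to 0.6 of it.

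**The case against.** The strongest reply is that the plan already offsets part of this. The mixed ANOVA is given only the group, time and interaction effects; no T2 contrast from it is specified. The only stated comparison of changes is the one-way ANOVA, and on a T1-to-T2 change it keeps someone who misses only T3. A reader might infer that anyone missing T2 or T3 disappears from the whole analysis. The document does not support that: it holds for the mixed and repeated-measures ANOVAs, not necessarily for the change test. The offset is incomplete, though. The visits for the change are not stated, a T1-to-T3 change has no value for anyone missing T3, and the group × time test still uses completers only.

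A reader might also infer that completer analysis overstates the training effect at both T2 and T3. That needs dropout driven by low gain in the training arm alone. Other equally plausible rules give no bias, bias at T2 only, or understatement, and nothing in the document points to one of them.

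Three further limits stand. No dropout is reported, so the harm may be nil. At 10% dropout the bias is small beside the sampling error. The within-group repeated-measures ANOVA is not a group comparison, so for that test the point concerns discarded data and selected completers, not a distorted contrast between arms.

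**Conclusion.** The point holds as a conditional one. The mixed and repeated-measures ANOVAs, as named, use complete T1-T2-T3 records only, and the plan contains nothing that restores the discarded visits. SPSS can fit a model that keeps partial records, but the text names ANOVA and not such a model.

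If all 39 complete, nothing changes. At an assumed 10% loss per visit, about 32 of 39 are complete while about 35 have T2, so roughly three or four observed T2 results are discarded, worth about 5% on the T2 standard error. Bias in the group comparison is possible, not established. For a true 0.50 SD, the T2 estimate runs from about 0.39 to 0.68 SD over the mechanisms examined, with no fixed direction, and T3 is unbiased under some of them. These figures rest on assumed dropout, equal correlations of 0.7 and dropout that depends on observed values.

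This is a worthwhile and cheap improvement to the plan. It is not evidence that the trial's result is wrong or exaggerated.

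**What to change.** Replace the two-way mixed ANOVA and the within-group repeated-measures ANOVAs with one linear mixed model per outcome: SPSS MIXED, REML, group, visit and their interaction as fixed effects, unstructured covariance over the three visits, and Satterthwaite degrees of freedom. Include all randomised participants in their assigned arm, with every available visit. Take the T2 and T3 between-arm contrasts and the within-arm changes from that model. If the one-way ANOVA of changes is kept, name its visits and report how many participants in each arm contribute to it.

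The cost is SAP wording in the same software, approximate degrees of freedom at about 13 per arm, and slightly more complex output. With complete data the answers are almost the same as from the ANOVA. The model protects only when missingness depends on observed data: if people stay away because of an unseen T3 state, it is biased too. Participants with only T1 add little.

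### The between-group tests are valid without covariates, but a change score fixes the T1 slope at 1; adjusting for T1, age and education would usually be more precise, at little cost

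*Combined protocol and SAP*

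**What the plan says.** The Participants section states "Thirty-nine older adults (aged 60–80) with MCI were recruited". Under Methods, "Participants were randomly assigned (stratified by age and education) into three groups", and outcomes are assessed at T1 (baseline), T2 (after training) and T3 (one month later). Objective 1 begins "To compare gait variables and global cognitive functions across the three groups before" and goes on to the later assessments.

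The Statistical Analysis Plan has two analyses that compare groups. One is a two-way mixed ANOVA with group, time and their interaction, in which T1 is one level of the outcome. The other is given as "one-way ANOVA was used to compare mean changes between groups". A repeated measures ANOVA covers within-group change only. No planned analysis names T1, age or education as a covariate or factor. The documents state no SD, correlation, effect size, power or allocation ratio, and do not define the interval over which change is taken.

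**The concern.** A change score does adjust for T1, but with an assumed slope of 1 rather than an estimated one. If the slope is lower, which with equal SDs means whenever the T1-follow-up correlation is below 1, the change score over-corrects: the arm that starts higher by chance is penalised too much. If the slope is above 1, it under-corrects. The same applies to the T1-based contrasts inside the group × time term.

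With 39 participants in three arms, chance imbalance at T1 can be sizeable and precision is scarce. The data needed to do better are already collected. There are several outcomes (gait variables under single- and dual-task walking, and MoCA), so a correlation near 1 cannot be presumed for all of them.

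**Working it through.** The documents contain no figure to reproduce, so this check is algebra under stated assumptions.

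**Inputs.** From the documents: N = 39, three arms, three visits, significance level 0.05. Assumed: 13 per arm, no dropout, change taken from T1, equal correlation ρ between visits, equal SDs unless stated, and two-sided pairwise tests. The full model is T1 plus age and education, one term each, with no prognostic value.

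**Conditional shift.** Let β = ρ × SD(follow-up)/SD(T1). Given a T1 difference d between two arms, the change-score contrast has mean effect + (β−1)d, a shift of size (1−β)d. One standard error of a pairwise T1 difference is √(2/13) = 0.39 SD. With equal SDs β = ρ, so an imbalance of that size shifts the contrast by 0.20, 0.12 and 0.04 SD at ρ = 0.5, 0.7 and 0.9.

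Conditional type I error of the pairwise change test (normal approximation):

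| T1 imbalance | ρ = 0.5 | ρ = 0.7 | ρ = 0.9 |
|---|---|---|---|
| none | 2.4% | 3.4% | 4.4% |
| 1 SE | about 5% | about 5% | about 5% |
| 2 SE | 13% | 10% | 7% |

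An imbalance of 2 SE or more arises in about 5% of randomisations for a given pair, and in 11% for at least one of the three pairs. Over all randomisations, simulated type I error of the one-way ANOVA on change was 4.8 to 5.2% for ρ from 0.3 to 0.9, the same as ANCOVA within simulation error.

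**Precision at T2.** Per-subject variances are 2(1−ρ) for change and 1−ρ² after T1 adjustment, so their ratio is (1+ρ)/2. Estimating the slopes multiplies this by 1 + 1/34 (T1 only) or 1 + 3/32 (full model). For the average of T2 and T3, the variances are 1.5(1−ρ) for mean(T2,T3) − T1 and (1+ρ)/2 − ρ² after adjustment; their ratio is (1+2ρ)/3, times the same factor.

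| Adjusted/unadjusted variance | 0.5 | 0.7 | 0.8 | 0.9 | 0.95 | Break-even ρ |
|---|---|---|---|---|---|---|
| T2, T1 only | 0.77 | 0.88 | 0.93 | 0.98 | 1.00 | 0.94 |
| T2, full model | 0.82 | 0.93 | 0.98 | 1.04 | 1.07 | 0.83 |
| T2-T3 average, full model | 0.73 | 0.88 | 0.95 | 1.02 | 1.06 | 0.87 |

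To match T1-only ANCOVA with 39 participants, the change score would need 39/0.772 ≈ 51 at ρ = 0.5, or 39/0.875 ≈ 45 at ρ = 0.7. Age and education repay their two degrees of freedom if they explain 1 − (1+1/34)/(1+3/32) = 0.059, about 6%, of the T1-adjusted variance.

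**Unequal SDs.** With k = SD(follow-up)/SD(T1), the T2 ratio is k²(1−ρ²)/(1+k²−2ρk) times the same factor. For the full model at ρ = 0.5, 0.7, 0.8 and 0.9 this gives 0.63, 0.69, 0.70, 0.67 at k = 0.8; 0.95, 1.06, 1.09, 1.07 at k = 1.2; and 1.00, 1.08, 1.09, 1.00 at k = 1.3. The T1-only ratio peaks at 1.03 in these cases.

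**Omnibus power**, arm effects 0, 0.35 and 0.7 SD (noncentral F):

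| Test | 0.5 | 0.7 | 0.8 | 0.9 |
|---|---|---|---|---|
| *Effect the same at T2 and T3* | | | | |
| One-way ANOVA on T2 change | 31.5% | 49.4% | 67.6% | 93.8% |
| Full model at T2 | 37.3% | 52.1% | 68.0% | 92.7% |
| Planned 4-df group × time | 31.8% | 51.5% | 71.3% | 96.3% |
| T2-T3 average minus T1, 2 df, no covariate | 40.7% | 62.1% | 80.5% | 98.3% |
| Full model on T2-T3 average, 2 df | 53.0% | 68.0% | 82.4% | 98.0% |
| *Effect at T2 only, gone by T3* | | | | |
| Planned 4-df group × time | 32% | 51% | 71% | 96% |
| Full model on T2-T3 average, 2 df | 16% | 21% | 28% | 48% |

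For the average, only the step from the no-covariate row to the full-model row is due to covariates. The rest comes from choosing a 2-df contrast, and it depends on the effect lasting.

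**Group main effect.** It averages all three visits, so a sustained 0.7 SD effect becomes (0 + 0.7 + 0.7)/3 = 0.47 SD, two thirds of its size.

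**The case against.** A reader might infer that the planned tests are biased or invalid because they ignore T1. The documents do not support that. Both tests use T1, groups are randomised, and type I error over randomisations is nominal as far as omitted covariates go. Nor does leaving out the strata inflate error. In simulations with three assumed strata explaining 10, 20 or 30% of outcome variance, an ANOVA that ignored them had type I error of about 3.7, 2.5 and 1.0%, which is conservative. Sphericity is a separate matter: an uncorrected group × time test reached 7.6% when T2 and T3 were correlated at 0.9 and each at 0.5 with T1.

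The best defence is that this is a choice between valid methods whose benefit turns on a correlation and an SD ratio that the documents do not give. Across the cases examined the full model's T2 ratio runs from 0.63 to 1.09, so it can lose. The strata are not described either. With four or five covariate degrees of freedom in all, the multiplier is 1 + 4/31 = 1.13 or 1 + 5/30 = 1.17, and the T2 break-even falls to about 0.77 or 0.71. All of this stands and limits the claim. It does not remove it, because T1-only adjustment costs at most about 3% in these cases and saves 12 to 23% at ρ of 0.5 to 0.7 with equal SDs.

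It would also be too strong to say that the plan takes the group main effect as the treatment effect. The SAP names the interaction as well, so this is only a caution about reading the output. Finally, the available SAP text ends without a full stop, so more may have followed; nothing available shows a covariate.

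**Conclusion.** The point holds as an improvement in efficiency and conditional bias that should be made because it is cheap. With 13 per arm and equal SDs, T1-only adjustment cuts T2 variance by 23% at ρ = 0.5 and 12% at 0.7, with little left at 0.9. The full model gains at T2 up to ρ = 0.83 and on the T2-T3 average up to 0.87, or further if age and education are prognostic. It can lose about 7% at ρ = 0.95, or about 9% if the follow-up SD is 20-30% larger and ρ is about 0.8. Every size here rests on assumed values, so confidence is moderate. The recommended mixed model was not itself simulated; ANCOVA on the mean of T2 and T3 stood in for it.

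**What to change.** Replace the one-way ANOVA on change with a model of T2 and T3 together (SPSS MIXED): group, visit, group × visit, T1, T1 × visit, age and education, with an unstructured covariance. Report adjusted group differences with 95% CIs at each visit. Before pairwise comparisons, keep an overall group test that does not depend on the effect persisting to T3. The planned group × time test would serve, or a joint test of group and group × visit in the adjusted model (power not computed here). Present the T2-T3 average only as a summary for a sustained effect. Do not read the mixed-ANOVA group main effect as the intervention effect, and give T1 values by group descriptively.

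The cost is SAP wording, one error degree of freedom for T1, and at least two for age and education (more if the strata need more terms). No new data are needed. Recruitment and some of the analyses are described in the past tense, so if the analysis is already done, report this as a labelled additional analysis.
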